9. ENDPOINT EVALUATION

9.1. Primary Endpoint

The primary endpoint is the NAC TNSS AUC_{0-1hr} at year 3, one year after completion of treatment.

[figure not shown]
9.1.1. Computation of the Primary Endpoint

The NAC TNSS AUC_{0-1hr} will be calculated as follows using the linear trapezoidal rule, for each visit the NAC is performed. The primary endpoint is the calculated AUC at the year 3 visit.

$$AUC = \sum_{i=1}^n \frac{TNSS_{i-1} + TNSS_i}{2(t_i - t_{i-1})}$$

where $TNSS_i$ = TNSS at time i , n is the number of timepoints being summed through the 1 hour timepoint, and $(t_i - t_{i-1})$ is the nominal time difference in hours between timepoint i and timepoint $i - 1$ for each of the intervals in the time span.

For the first timepoint of the interval, the post-lavage result will be used. This will only be used to establish a starting count to calculate first area under curve (the first element in the summation). An illustration of the AUC calculation (as shown by the shaded area) is presented below.

If the last timepoint for 1 hour is missing for a participant included in the primary endpoint analysis, then linear interpolation will be used to impute the missing value using a weighted average of TNSS for the time points on either side, weighted by their relative distance from the nominal time point over the distance between them. This is equivalent to connecting the prior and subsequent values to the missing value (at 30 minutes and 7 hours, respectively) and calculating where the 1 hour value would fall on that line.

9.1.2. Primary Analysis of the Primary Endpoint

The primary analysis will compare the mean TNSS AUC_{0-1hr} between treatment arms using a longitudinal repeated measures model on data from the mITT sample at years 1, 2, and 3. The model will include fixed effects for treatment arm (all 3 levels), time (i.e. year), and treatment arm by time interaction and will include a covariate for baseline TNSS AUC_{0-1hr}. Since a nonlinear relationship between TNSS AUC_{0-1hr} and time is expected, time will be treated as a categorical variable (with 3 levels = year 1, year 2, and year 3).

The covariance parameters for the model will be estimated using residual (restricted) maximum likelihood (REML) estimation, and the Kenward-Roger method will be used to compute the denominator degrees of freedom. An unstructured covariance matrix will be assumed to model the correlation among time points within a participant. If convergence issues are experienced with this matrix type, then Toeplitz, first-order auto-regressive, and compound symmetry types will be tried in order and the first matrix to result in successful convergence will be used. If all three alternative matrix types converge, then the best fitting and most parsimonious model may be investigated and chosen as the most suitable model.

The LS means with associated 95% confidence intervals (CIs) will be reported for each treatment arm and time point. Finally, the LS means treatment difference at each time point (year 1, 2, and 3) with associated two-sided p-value will be reported for each pairwise difference:

- Combination of SLIT and dupilumab arm *versus* double-placebo arm
- SLIT plus dupilumab placebo arm *versus* double-placebo arm
- Combination of SLIT and dupilumab arm *versus* SLIT plus dupilumab placebo arm

The primary objective will be addressed by the LS means treatment difference at year 3 between the combination of SLIT and dupilumab arm *versus* double-placebo arm.

Diagnostics for the validity of the primary endpoint analysis will be conducted. Specifically, to assess if the normality assumptions for the longitudinal repeated measures model are met, departures from normality will be investigated by inspecting the model residuals (including a quantile-quantile plot, histogram of residuals, etc.). If the normality assumption is violated, then another suitable statistical technique will be considered, for example including log-transforming the AUC values prior to modeling or performing a non-parametric test.

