13.6 SAMPLE SIZE CONSIDERATIONS

Sample size for this trial was determined by calculating the total enrollment necessary to provide at least 80% power to detect an expected difference in the mean TNSS AUC_{0-1hr} at year 3 comparing the combination of SLIT and dupilumab arm to the double-placebo arm.

Estimates used for this sample size calculation are based on the mean in the placebo arm (3.81) and a range of standard deviations for TNSS AUC_{0-1hr} observed in the GRASS study²⁰: placebo (1.73), SLIT (1.53), and pooled placebo and SLIT arms (1.64).

Using this range of standard deviations and an ANOVA test with a two-sided alpha level of 0.05, a total of 90 participants with TNSS AUC_{0-1hr} at year 3 (30 participants per arm) will allow us to detect a reduction of at least 29% - 33% in the mean TNSS AUC_{0-1hr} at year 3 between the combination of SLIT and dupilumab and double-placebo arms. This exceeds the 20% minimally clinically important difference recommended by the WAO.

Assuming 6 participants per arm (16.6%), will not complete the NAC assessment at year 3, a total sample size of N=108 randomized participants who receive at least one dose of study drug and complete the NAC assessment at baseline is required. This assumed discontinuation rate approximates and is slightly more conservative than the discontinuation rate observed in the GRASS study (13.2%).

Repeated measures analysis (as is planned for the primary analysis of the primary endpoint) provides more statistical power than cross-sectional analysis, since the greater total number of observations over all participants and time points increases the degrees of freedom available for hypothesis tests. Hence, with the current sample size, the power to detect the stated differences is anticipated to be greater than 80%.

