9.2. Secondary Endpoints

All secondary endpoints denoted as “key” per the multiplicity control testing algorithm (see [Section 8.5](#)) are alpha-controlled. The remaining secondary endpoints, including time points and pairwise comparisons that do not appear explicitly in Table 2: Endpoints with Multiplicity Control of this SAP, will be treated as supportive and are not alpha-controlled; therefore p-values are to be treated as descriptive only.

Unless otherwise noted, all secondary endpoint analyses will be performed on data from the mITT sample using a similar model methodology as per the primary endpoint analysis as described in [Section 9.1.2](#) above. All the same model stipulations apply including the inclusion of fixed effects for treatment arm (all 3 levels), time (i.e. year), and treatment arm by time interaction. Any additional baseline covariates that apply for a given secondary endpoint are noted in each sub-section below.

All pairwise treatment differences will be presented for each year post-treatment, as estimated by the models. Unless otherwise specified, the secondary endpoints will focus on the comparison for:

- Combination of SLIT and dupilumab arm *versus* double-placebo arm

The exploratory endpoints will focus on the remaining pairwise treatment comparisons (see [Section 9.3](#)).

Clinical tolerance endpoints will come from the model estimates at year 3, one year after completion of study treatment; whereas clinical desensitization endpoints will come from the model estimates at year 1 and 2 whilst on study treatment.

If a large departure from normality is found from model assumption testing, then log-transforming the outcome variable of interest prior to modeling or switching to a non-parametric test at each time point, may be performed instead.

9.2.1. TNSS AUC_{0-1hr} at years 1 and 2

The same model as for the primary analysis of TNSS AUC_{0-1hr} above will be used to estimate the LS means treatment difference at years 1 and 2 for the pairwise treatment difference between the combination of SLIT and dupilumab arm *versus* double-placebo arm.

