9.4. Examination of Subgroups

All subgroup examinations will be exploratory in nature, with a purpose to explore the uniformity of any treatment effects found overall.

First, subgroup analyses of the primary endpoint will include repeating the primary analysis of the primary endpoint using a longitudinal repeated measures model adjusting for treatment arm, time, baseline TNSS AUC_{0-1hr}, and the baseline ratio of grass pollen specific-IgE to total IgE. An interaction term will also be included between the ratio of grass pollen specific-IgE to total IgE and treatment arm, to evaluate if the treatment effect on the primary endpoint is modified by differing levels of the ratio of grass pollen specific-IgE to total IgE. The interaction effect between the treatment group and the subgroup variable will be tested using a Type III fixed effects test.

The same modeling approach will be employed to evaluate if the treatment effect on the primary endpoint is modified by differing levels of:

- baseline grass pollen specific-IgE (i.e. the values alone, not as a ratio to total IgE)
- baseline grass pollen skin prick test wheal size (mm).

Second, subgroup analyses of the primary endpoint will repeat the primary analysis model for the primary endpoint using a *separate* model for each subgroup level. Repeat for the following subgroup levels:

- Age (years): $<$ median and \geq median
- Sex: male and female
- Race: white, black, Asian, mixed, and other (including unknown/not reported); race categories that have a low sample size may be combined

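### The covariance fallback in SAP 9.1.2 gives two conflicting selection rules and names only equal-variance structures, so type I error at year 3 would not be held at 5% if it were used

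*SAP*

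**What the plan says.** Protocol 13.3.2 specifies an unstructured covariance for the primary model and no fallback. SAP 9.1.2 keeps that choice, with REML and Kenward-Roger degrees of freedom, and adds a fallback for convergence problems. Toeplitz, first-order autoregressive (AR(1)) and compound symmetry (CS) are tried in that order, and "the first matrix to result in successful convergence will be used". The following sentence reads "If all three alternative matrix types converge, then the best fitting and most parsimonious model may be investigated" and then chosen. No fit criterion, heterogeneous-variance version or robust standard error is named.

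The rule reaches beyond the primary endpoint. SAP 9.2 says of the secondary models: "All the same model stipulations apply including the inclusion of fixed effects for treatment arm". SAP 9.4 refits the primary model separately by age, sex and race level. SAP 8.4 places the final analysis after database lock, with unblinded treatment data.

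**The concern.** There are two separate faults.

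**Selection.** The first sentence ends the search at the first converged structure. The second can apply only if all three have been fitted, and it then allows a different one to replace the first. When all three converge, the first sentence always gives Toeplitz, while the second may give AR(1) or CS. With no criterion named and treatment unblinded, the text permits more than one primary p-value.

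**Equal variance.** As named, each fallback has a single variance for years 1, 2 and 3. Only year 3 is primary, and it is the only year off treatment. The standard error of the year-3 contrast would then reflect roughly the average variance over the three years. Kenward-Roger does not correct a misspecified covariance model.

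At stake, if a fallback is used, are the standard error, confidence interval and p-value of the year-3 contrast.

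**Working it through.** **Inputs from the documents (Protocol 13.6).** Placebo mean 3.81; SDs 1.73 (placebo), 1.53 (SLIT) and 1.64 (pooled); 36 per arm with 30 assessed at year 3; "an ANOVA test with a two-sided alpha level of 0.05"; at least 80% power. No SD by year is given anywhere.

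**The plan's own figure.** Detectable reduction = SD × √(2/30) × (1.960 + 0.842) / 3.81.
- SD 1.53: 29.05%
- SD 1.73: 32.85%

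This reproduces the stated 29%–33%. Likewise 30 / (1 − 6/36) = 36 per arm, or 108 in total. The design figures are sound; they do not bear on the fallback.

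**Closed form for an equal-variance fallback.** With complete data and a mean for every arm and year, the true variance of the year-3 contrast is proportional to s₃². The model reports approximately (s₁² + s₂² + s₃²)/3. Hence

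type I error = 2 × [1 − Φ(1.96 × √(mean variance / s₃²))].

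Assumed SDs for years 1/2/3, the same in all arms:
- 1.53/1.53/1.73: mean variance 2.558, divided by 2.993 = 0.855, root 0.925, critical value 1.812, error **7.0%**
- 1.3/1.3/1.7: 2.090 / 2.890 = 0.723, root 0.850, critical value 1.667, error **9.6%**
- 1.0/1.0/1.7: 1.630 / 2.890 = 0.564, root 0.751, critical value 1.472, error **14.1%**
- 1.7/1.7/1.3: 2.490 / 1.690 = 1.473, root 1.214, critical value 2.379, error **1.7%**

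If only the two active arms have a lower SD in years 1 and 2 (ratio r to year 3), the pooled variance relative to year 3 is [2 × (2r² + 1)/3 + 1]/3. At r = 0.60 this is 0.716, giving 9.7%.

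**Simulation.** REML fits to 2,000 trials per scenario: 36 per arm, 6 per arm lost before year 3, baseline covariate, arm-by-year means. A t reference on fixed degrees of freedom (86 for unstructured, 150 for the others) stood in for Kenward-Roger. Monte Carlo standard error is about 0.5 to 0.8 points.

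| SD in years 1–2 ÷ SD in year 3 | Arms affected | Closed form | Toeplitz, AR(1), CS (simulated) | Unstructured (simulated) |
|---|---|---|---|---|
| 1.00 | – | 5.0% | 5.4–5.6% | 5.3% |
| 0.88 | all | 7.0% | 7.3–7.6% | 5.3% |
| 0.88 | active only | 6.3% | 6.9–7.5% | 5.6% |
| 0.75 | all | 9.9% | 9.4–9.5% | 4.7% |
| 0.75 | active only | 7.9% | 7.5–7.8% | 4.8% |
| 0.60 | all | 13.8% | 13.4–14.6% | 4.5% |
| 0.60 | active only | 9.7% | 9.6–9.8% | 4.4% |
| 1.13 | all | 3.3% | 2.7–3.2% | 4.4% |

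Two further results:
- Choosing among the three fallbacks by AIC changed the rejection rate by no more than about 1 point from any single structure.
- The unstructured fit failed in 0 of 8 × 2,000 = 16,000 simulated trials.

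**Check of the remedy.** In a separate simulation (SDs 1.3/1.3/1.7, correlation 0.5, 30 per arm at year 3, 1,500 runs), Toeplitz rejected 9.7% and heterogeneous Toeplitz 5.3%.

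**The case against.** **The fallback will probably not be reached.** Unstructured is the specified model. A 3 × 3 matrix on about 108 participants should converge, and it did in every simulated trial. This stands, and it largely disposes of any practical effect on the primary test. The simulated data were well behaved, so it shows that failure is unlikely, not that it is impossible.

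**The inflation rests on assumed SDs.** This also stands. A reader might take 1.53 and 1.73 as the plan's range over years, but Protocol 13.6 gives them as SLIT-arm and placebo-arm SDs, so the 7% figure borrows a between-arm ratio. The 14% end needs SDs about 40% lower in years 1 and 2 in every arm, including double placebo, which receives no active drug in any year. Protocol 1.2 reports about a 30% reduction in a longer-window TNSS AUC on SLIT and 7% after withdrawal. That makes a change in spread plausible, but those are differences in means, not SDs. The error can equally be conservative.

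**The contradiction does not cause the inflation.** Correct. The inflation comes from the equal-variance list; the selection rule moved the rate by only about 1 point.

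**The reach is limited.** CSMS and miniRQLQ have their own fallback (SAP 9.2.6, 9.2.7), and its example, UN@AR(1), keeps year unstructured. Sneeze count uses a different model (9.3.2). The remaining secondary models have the same three time points. The subgroup refits are more exposed to small samples, but they are exploratory, and "race categories that have a low sample size may be combined".

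What survives is the conflict in the text and the lack of a separate year-3 variance in every named fallback.

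**Conclusion.** The point holds as a low-priority specification fault. SAP 9.1.2 does not determine which fallback is used, and none of the named fallbacks protects the year-3 test against variances that differ by year. Conditional on a fallback being used, the type I error ranges from about 2% to about 14%, with 5% at equal SDs. Where in that range it falls depends on SDs by year that the documents do not give.

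A reader might infer that the trial's primary test runs at 7–14%. The documents do not support that. The figure requires the unstructured fit to fail and the year-3 SD to be the larger one. Nor do the documents say that a fallback was used. The post-lock note at the end of the SAP records one change, to the AUC formula, and says nothing about covariance.

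**What to change.** Replace the list with heterogeneous-variance structures under REML and Kenward-Roger: heterogeneous Toeplitz (TOEPH), then heterogeneous AR(1) (ARH(1)), then heterogeneous compound symmetry (CSH). Take the first that converges, and delete the sentence that applies when all three converge.

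The wording change is one sentence. The statistical cost is two extra variance parameters at three time points: TOEPH 5 against Toeplitz 3, ARH(1) 4 against AR(1) 2, CSH 4 against CS 2. TOEPH is only one parameter short of the unstructured 6, so data that defeat the unstructured fit may defeat it too, and the later steps may be needed.

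Because the database is locked, a rewritten rule would be a post-lock change to the primary analysis. The practical step is to report which covariance structure each model used under 9.1.2, 9.2 and 9.4, and to add the heterogeneous-variance result wherever an equal-variance fallback was used. If every model converged as unstructured, one sentence in the study report closes the point.

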9.1.3. Sensitivity Analyses of the Primary Analysis

The following sensitivity analysis will be conducted on the primary estimand, by changing the handling of intercurrent events as follows:

1. Hypothetical strategy assuming missing at random
 - a. For this sensitivity analysis, a hypothetical strategy will be used such that any missing post-baseline assessments will be imputed using multiple imputation (MI), assuming Missing at Random (MAR) for participants with monotone missing data due to early study discontinuation. Intermittent missing data will first

be imputed using the Markov Chain Monte Carlo (MCMC) method which is appropriate for non-monotonic missing data, with imputations done by treatment arm and adjusted for baseline covariates. Monotone missing data (i.e., data missing after participants discontinue the study early) will then be multiply-imputed using a regression method adjusting for treatment arm, baseline TNSS AUC_{0-1hr} and other baseline covariates as appropriate. There will be 100 samples imputed for this MI analysis, and results will be summarized across the 100 MI samples. The overall estimate will be compared to the estimate derived from the primary estimand model to assess the potential magnitude and direction of bias.

2. Hypothetical strategy assuming missing not at random

- a. For this sensitivity analysis, a hypothetical strategy will be used such that any missing post-baseline assessments will be imputed using multiple imputation (MI), assuming Missing Not at Random (MNAR) for participants with monotone missing data due to early study discontinuation. The same first MCMC step will be carried out for non-monotonic missing data, as described above. However, for the second step for multiple imputation of the monotone missing data, the MI data will be modelled from data of similar participants from the double-placebo arm following the “copy reference” approach. This hypothetical strategy assumes that active treatment participant values follow that of the double-placebo group after early study discontinuation.

In addition to the above model-based methods of exploring the impact of missing data, demographic characteristics and baseline assessments among subgroups defined by study completion status (completers versus early discounters) will be summarized to identify possible differences of interest.

9.1.4. Supportive Analyses of the Primary Endpoint

The primary analysis of the primary endpoint will be repeated in the same manner as above, but using participants included in the PP sample instead.

For both mITT and PP samples, a plot of LS means (with associated 95% CI) for TNSS AUC_{0-1hr} for each treatment arm will be plotted by year to illustrate the treatment effects over time. For the mITT sample, this same plot will additionally be repeated using the LS means and 95% CI from the first MI model above assuming MAR.

9.2. Secondary Endpoints

All secondary endpoints denoted as “key” per the multiplicity control testing algorithm (see [Section 8.5](#)) are alpha-controlled. The remaining secondary endpoints, including time points and pairwise comparisons that do not appear explicitly in Table 2: Endpoints with Multiplicity Control of this SAP, will be treated as supportive and are not alpha-controlled; therefore p-values are to be treated as descriptive only.

Unless otherwise noted, all secondary endpoint analyses will be performed on data from the mITT sample using a similar model methodology as per the primary endpoint analysis as described in [Section 9.1.2](#) above. All the same model stipulations apply including the inclusion of fixed effects for treatment arm (all 3 levels), time (i.e. year), and treatment arm by time interaction. Any additional baseline covariates that apply for a given secondary endpoint are noted in each sub-section below.

All pairwise treatment differences will be presented for each year post-treatment, as estimated by the models. Unless otherwise specified, the secondary endpoints will focus on the comparison for:

- Combination of SLIT and dupilumab arm *versus* double-placebo arm

The exploratory endpoints will focus on the remaining pairwise treatment comparisons (see [Section 9.3](#)).

Clinical tolerance endpoints will come from the model estimates at year 3, one year after completion of study treatment; whereas clinical desensitization endpoints will come from the model estimates at year 1 and 2 whilst on study treatment.

If a large departure from normality is found from model assumption testing, then log-transforming the outcome variable of interest prior to modeling or switching to a non-parametric test at each time point, may be performed instead.

9.2.1. TNSS AUC_{0-1hr} at years 1 and 2

The same model as for the primary analysis of TNSS AUC_{0-1hr} above will be used to estimate the LS means treatment difference at years 1 and 2 for the pairwise treatment difference between the combination of SLIT and dupilumab arm *versus* double-placebo arm.

9.2.2. Delta PNIF AUC_{0-1hr}

Peak nasal inspiratory flow, defined as the change in PNIF relative to the pre-allergen exposure PNIF measurement during the NAC (Delta PNIF AUC_{0-1hr}), will be analyzed using a longitudinal repeated measures model on data from years 1, 2, and 3 with a covariate for baseline Delta PNIF AUC_{0-1hr}. All model details per the primary endpoint analysis apply.

For each year's visit, the first step will be to calculate the change in PNIF by subtracting the post-lavage value at each "post" time point, as follows:

$$\text{Change in PNIF } (L/\text{min})_{\text{timepoint } x} = (PNIF_{\text{timepoint } x} - PNIF_{\text{post-lavage}})$$

The change in PNIF will be calculated this way for all time points starting with “5 minutes post”. Then, the AUC_{0-1hr} will be calculated using all available change in PNIF values through the 1 hour time point, using the trapezoidal rule in the same manner as stated in [Section 9.1.1](#). To establish a starting count to calculate first area under curve (the first element in the summation), a change value of 0 will be used. The same linear interpolation details apply if a participant is missing their change in PNIF for the 1 hour time point.

